TAP Block Study

NCT05537883

IRB Approval Date: 07AUG2023

Study Title: Single Blinded Randomized Trial of Transversus Abdominis Plane Block Using Liposomal Bupivacaine in Metabolic and Bariatric Surgery Patients

Principal Investigator: [name]

Co-Investigators: [name], [name]

Sponsor or funding source: Wake Forest University Health Sciences

Background, Rationale, and Context

The transversus abdominis plane (TAP) block was described in 2007 using an ultrasound to inject local anesthetic between the internal oblique and transversus abdominis muscles where the sensory nerves of the abdominal wall travel [1]. The TAP block can also be performed by the surgeon with laparoscopic guidance. TAP block has been shown to provide analgesia after abdominal surgery, decreasing opioid use, and is widely accepted into practice [2]. TAP block has become a cornerstone in enhanced recovery after surgery programs, as well as part of multimodal analgesia, and opioid reducing efforts nationwide. A recent meta-analysis of Randomized Controlled Trials (RCT) comparing TAP block with bupivacaine or ropivacaine to no TAP block in bariatric surgery showed reduced postoperative nausea and vomiting and time to ambulation [3]. Liposomal bupivacaine compared to plain bupivacaine has been touted to provide a longer duration of analgesia (up to 72 hours) by slowly releasing the anesthetic agent into local tissue. A recent systematic review comparing liposomal bupivacaine to conventional local anesthetic agents in regional anesthesia, including TAP blocks, showed conflicting results so no definitive conclusions could be made [4]. It is unclear if liposomal bupivacaine is superior to plain bupivacaine for TAP blocks in bariatric surgery. Our study would be the first RCT comparing laparoscopic TAP block with liposomal bupivacaine vs plain bupivacaine in a bariatric surgery population.

Objectives

Compared to only Bupivacaine administered via TAP block, we will investigate the analgesia effects to patients undergoing metabolic and bariatric surgery receiving TAP block with a Liposomal Bupivacaine mixture.

Primary Objective: To determine if patients undergoing metabolic and bariatric surgery receiving TAP block with a Liposomal Bupivacaine results in pain scores, as measured by visual analogic scale (VAS), that are equivalent compared to patients receiving TAP block with Bupivacaine only.

Primary Hypothesis:

- 1) Lower values of the outcome variable VAS are desirable, and the hypothesis is listed below –

Hypothesis 1. 1

$H_0: \mu_E - \mu_S \geq \delta$ (Study group is different compared to the active control group by δ or more)

$H_1: \mu_E - \mu_S < \delta$ (Study group is equivalent to the active control when difference is within prespecified δ)

Where μ_E, μ_S are the population means for the outcome VAS measured at 24 hours after surgery for the study group (E) and the standard (S) active group, respectively

δ is non-inferiority margin, specified in advance based on clinical judgement. Based on our clinical experience, $\delta = 1.5$

Secondary Objectives: Compared to TAP block with Bupivacaine only, we will compare opioid consumption, and other effect differences to patients undergoing metabolic and bariatric surgery receiving TAP block with Liposomal Bupivacaine.

Secondary Hypotheses

Hypothesis 2.1 – Patients undergoing metabolic and bariatric surgery receiving TAP block with Liposomal Bupivacaine results in less opioid consumption before hospital discharge /during the first 48 hours postoperatively as measured in morphine equivalents (mg) compared to patients receiving simply TAP block with Bupivacaine only.

Hypothesis 2.2 - Patients undergoing metabolic and bariatric surgery receiving TAP block with Liposomal Bupivacaine results in pain score as measured by visual analog scale (VAS) at 12 hours after surgery that are equivalent compared to patients receiving TAP block with Bupivacaine only.

Exploratory objectives: We will explore other effects, including pain score at 48 hours, and 72 hours after surgery, total opioid consumption required post op during their one-week post op visit as measured in morphine equivalences.

Methods and Measures

Design

This study is a 2-arm parallel single blinded randomized equivalency, single-center, clinical trial. Patients will be blinded to type of TAP block used.

Setting

This study will take place at Atrium Health, an academic medical center.

Subjects selection criteria

Inclusion Criteria

To be eligible for enrollment in this study, participants must meet all the following criteria:

1. Adult, age > 18 years
2. Participants who can give written informed consent and willing to comply with all stud-related procedures.
3. Patients undergoing primary sleeve gastrectomy or roux-en-y gastric bypass

Exclusion Criteria

1. Patients undergoing duodenal switch procedures
2. Patients undergoing concomitant hiatal hernia repair or ventral hernia repair or cholecystectomy at time of primary metabolic surgery
3. Patients with chronic opioid use

Sample Size

The number of patients required in each group is determined from a power analysis based on primary hypothesis.

In this study, based on our clinical experience, we assume standard deviation for each group is 3, the margin of equivalence is 1.5 on NRS, and the true difference between the two groups is 0 on the NRS. Group sample size of 88 from each group achieves 90% power to detect our prespecified equivalence margins, with alpha of 0.05. Assuming a 20% dropout or withdrawal based upon previous experience, 106 subjects per group will be required.

Interventions and Interactions

There will be two groups: (1) active control and (2) study group. Active control group patients receive TAP block with a Bupivacaine only mixture, containing 50 mL 0.5% Bupivacaine, and 100 mL normal saline solution. Study group patients will receive TAP block with a Liposomal Bupivacaine mixture, containing 20 mL Liposomal Bupivacaine, 30 mL 0.5% Bupivacaine, and 100 mL normal saline solution. TAP block technique will be standardized using subcostal as well as anterior axillary line as landmarks, injecting down to level of T10, using laparoscopic-guided approach. TAP block will be administered at the start of every case, after the first port is placed upon laparoscopy. Type of anesthesia administered will also be standardized including the use of narcotics, lidocaine, inhalational anesthesia and Ketamine.

Randomization schedules will be generated by SAS 9.4 (SAS Institute Inc., Cary, NC) by using a masked block randomization procedure. Eligible patients will be randomized with a 1:1 ratio between the 2 groups of patients receiving TAP block Exparel mixture or simply bupivacaine administered via TAP block. Research Electronic Data Capture (REDCap) randomization

module will be used to manage randomization and allocate treatment groups. The allocation sequence will be concealed with application of the REDCap.

Outcome Measure(s)

Primary Outcome measures

1. Pain score at 24 hours post-operative, using visual analogue scale (VAS), ranging from 1 to 10. One indicates no pain, and 10 indicates the worst pain one could image.

Secondary Outcome Measures

1. Pain scores at 12 hours, 48 hours, and 72 hours post-operatively.
2. Morphine milligram equivalences consumed during hospital stay
3. Morphine milligram equivalences prescribed and consumed as measured at one week follow up clinic visit
4. Post-operative nausea and vomiting (PONV) measured by a numerical score (1: no nausea or vomiting, 2: some nausea no vomiting, 3: nausea and vomiting)
5. Length of stay in hours
6. Patient satisfaction score

These parameters will be scored via SeamlessMD on a phone application, as well as paper and pen on a standardized reporting form for patients less comfortable using technology. Data will also be collected from patient electronic charts.

Analytical Plan

Equivalency test with priori specified non-inferiority region will be used to assess primary outcome variables.

Descriptive statistics (mean, range, percentage, median, etc.) will be used to assess the quality and accuracy of the administrative and clinical data. Means with standard deviations or medians with interquartile range (IQR) will be reported for continuous variables and percentages for categorical variables. Missing data will be evaluated prior to data modeling. General linear regression, or other generalized linear regression models will be used to compare the outcomes between the two groups with both univariate or multivariate analyses. Potential confounders will be identified with univariate analysis. For univariate analyses, a Student's t-test or Wilcoxon two-sample test will be used for continuous variables, and chi-square test for categorical variables against the primary and secondary outcomes. Both unadjusted and adjusted odds ratio (OR) with

corresponding 95% confidence interval (CI) will be reported. Two-tailed p values will be calculated for all tests, and $p < 0.05$ is considered statistically significant. All data will be analyzed using Statistical Analysis Software, version 9.4 (SAS Institute Inc., Cary, NC).

There are no plans for interim data analyses. Analyses will be conducted according to per-protocol (PP) principle.

Human Subjects Protection

Subject Recruitment Methods

Patients who are scheduled for sleeve gastrectomy or roux-en-y gastric bypass will be identified and recruited for the study at the Atrium Health Weight Management clinics during their pre-operative visit. The bariatric surgeons and bariatric surgery fellows will do the recruiting, and patients will be contacted directly face to face during the preoperative visit about the study. Patients will also receive a written flyer containing information about the study during the preoperative visit. As all qualifying patients will be informed about the study during the preoperative visit, access to participation among women and minorities will depend on how many of these patients undergo sleeve gastrectomy or roux-en-y gastric bypass at our institution. Subject's privacy will be protected by storing records of Protected Health Information in locked facilities or password protected computers. Data will be stored on a password protected computer of the investigator and in a password protected RedCap database.

Informed Consent

Signed informed consent will be obtained from each subject. The investigators as well as the other bariatric surgeons and bariatric surgery fellows will obtain informed consent at the Atrium Health Weight Management clinics during the preoperative visit.

Confidentiality and Privacy

Confidentiality will be protected by collecting only information needed to assess study outcomes, minimizing to the fullest extent possible the collection of any information that could directly identify subjects, and maintaining all study information in a secure manner. To help ensure subject privacy and confidentiality, only a unique study identifier will appear on the data collection form. Any collected patient identifying information corresponding to the unique study identifier will be maintained on a linkage file, stored separately from the data. The linkage file will be kept secure, with access limited to designated study personnel. Following data collection subject identifying information will be destroyed (state the anticipated time the data will be destroyed, e.g. three years after closure of the study, and the method of destruction), consistent with data validation and study design, producing an anonymous analytical data set. Data access will be limited to study staff. Data and records will be kept locked and secured, with any computer data

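### The primary hypothesis is printed as a one-sided non-inferiority test with no bound at −1.5, although the plan claims equivalence

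*Combined protocol and SAP*

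**What the plan says.** The document is a combined protocol and SAP. On the primary comparison it says the following.

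- **Primary Objective:** pain scores, "as measured by visual analogic scale (VAS), that are equivalent compared to patients receiving TAP block with Bupivacaine only".
- **Primary Hypothesis, Hypothesis 1.1:** H0: μE − μS ≥ δ against H1: μE − μS < δ, with δ = 1.5 and lower scores stated to be better. The gloss on H1 reads "Study group is equivalent to the active control when difference is within prespecified δ". The gloss on H0 speaks of a difference of δ or more, without a direction. The margin itself is described thus: "δ is non-inferiority margin, specified in advance based on clinical judgement".
- **Secondary Hypotheses, Hypothesis 2.2:** the same equivalence claim, "at 12 hours after surgery that are equivalent compared to patients receiving TAP block with Bupivacaine only", with no formula and no margin of its own.
- **Design:** "This study is a 2-arm parallel single blinded randomized equivalency, single-center, clinical trial".
- **Sample Size:** "the margin of equivalence is 1.5 on NRS, and the true difference between the two groups is 0 on the NRS", with SD 3 in each group, and then "Group sample size of 88 from each group achieves 90% power to detect our prespecified equivalence margins, with alpha of 0.05".
- **Analytical Plan:** "Equivalency test with priori specified non-inferiority region will be used to assess primary outcome variables". It later calls for two-tailed p values throughout, with significance at p < 0.05. The only confidence interval it mentions is a 95% interval for odds ratios.

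**The concern.** Equivalence needs two bounds: the study arm must be neither worse nor better by the margin. The printed pair has only the first. Rejecting its H0 shows that the study arm is not worse by 1.5 or more, which is non-inferiority. A large benefit also satisfies the printed H1 and would be reported as equivalence.

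This is the decision rule for the primary endpoint, and two analysts could reach opposite conclusions from the same data. One following the formula tests one side. One following the words tests two sides but must still choose the level, because the plan gives an alpha of 0.05 without saying whether it applies per side and asks for two-tailed p values for every test. The background section treats superiority of liposomal bupivacaine as an open question, so a benefit cannot be dismissed as a possible result.

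**Working it through.** **Inputs.** Margin 1.5 (Hypothesis 1.1 and Sample Size); SD 3 per group, true difference 0, 88 per group, 90% power, alpha 0.05 (Sample Size); 1:1 allocation (Interventions and Interactions).

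Standard error = 3 × √(2/88) = 0.452, with 2 × 88 − 2 = 174 degrees of freedom. The noncentrality at a true difference of 0 is 1.5 / 0.452 = 3.317.

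**1. Reproducing the plan's 88.** The power of one one-sided t-test is the probability that a noncentral t (174 df, noncentrality 3.317) exceeds its critical value. At 5% this is 0.951. TOST requires both one-sided tests to reject, and by symmetry at a true difference of 0 its power is 1 − 2 × (1 − 0.9514) = 0.903. At 87 per group it is 0.899. So 88 is exactly the smallest number giving 90% power for TOST at 5% per side.

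**2. Power at a true difference of 0 under each reading.**

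| Rule | Power at 88 per group | Minimum per group for 90% |
|---|---|---|
| TOST, 5% per side (90% CI) | 90.3% | 88 |
| TOST, 2.5% per side (95% CI) | 81.9% | 105 |
| Printed one-sided test, 5% | 95.1% | 70 |
| Printed one-sided test, 2.5% | 91.0% | 86 |

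Only the first row matches 88 exactly at the stated alpha.

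**3. What the missing lower bound does.** This is the probability of declaring equivalence at 88 per group and 5% per side if the study arm is truly better:

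| True μE − μS | Printed test | TOST |
|---|---|---|
| −1.5 | > 99.9% | 5.0% |
| −2.0 | > 99.9% | 0.3% |

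In the same two cases an ordinary two-sided 5% t-test of no difference is significant 91.0% and 99.3% of the time. Every such result favouring the study arm also rejects the printed H0.

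**4. What the undefined level does.** With an observed SD of 3, the confidence-interval half-width is 0.748 (90%) or 0.893 (95%). The largest observed difference that passes equivalence is then 1.5 − 0.748 = 0.752 or 1.5 − 0.893 = 0.607. An observed difference between about 0.61 and 0.75 in either direction passes one rule and fails the other.

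**The case against.** The strongest reply is that the intention is clear. The objective, the glosses on H0 and H1, the Design, the sample-size wording and the named equivalence test all point to two sides, and TOST at the stated 0.05 reproduces 88. On that view the formula and the margin's label are slips, and the level can be inferred. This largely stands as a reading of intent. It means that the formula is wrong, and a confirmatory rule should not have to be inferred from a sample-size match. The call for two-tailed p values sits with the regression and t-test methods, but it is worded to cover all tests, so the level for the primary test remains open.

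Three further points are fair.

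- The number 88 does not by itself exclude non-inferiority, since a one-sided 2.5% test needs 86. The conflict with the sample size lies in its wording and stated alpha.
- The figures for a true benefit of 1.5 or 2 points are conditional. At the assumed difference of 0, the printed test and TOST differ by only about 5 percentage points (95.1% against 90.3%).
- An equivalent result with p < 0.05 is not peculiar to the printed formula. A correct TOST at 88 per group can give both when the observed SD is below about 2.74, so that coincidence alone is not evidence of error.

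Absolute-value bars could have been lost when the PDF was read. The non-inferiority label and the stated direction of benefit fit a one-sided pair, however. Even with the bars restored, the labels would conflict and no decision rule would be stated.

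**Conclusion.** The concern holds and must be fixed. As printed, the primary test has no bound at −1.5 and contradicts its own gloss, the primary objective, the Design and the sample-size wording. The Analytical Plan joins the two frameworks in one sentence and does not settle the matter. Followed literally at one-sided 5%, the rule would almost always label a true benefit of 1.5 points or more as equivalence. Followed in words, the test has 90.3% or 81.9% power at 88 per group, depending on a level that the plan does not state.

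These figures assume SD 3, equal groups of 88 evaluable patients and t-based tests. The contradiction does not depend on them. That two-sided equivalence at 5% per side was intended is an inference, though a well-supported one.

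**What to change.** - In Hypothesis 1.1, write H0: |μE − μS| ≥ 1.5 against H1: |μE − μS| < 1.5.
- State the rule: two one-sided t-tests at 5% per side, with equivalence concluded only if the 90% confidence interval for μE − μS lies wholly within −1.5 to +1.5.
- In Hypothesis 1.1 and the Analytical Plan, replace the non-inferiority label with an equivalence margin of ±1.5. State that this rule, and not the general two-tailed p < 0.05, governs the primary outcome.
- Put Hypothesis 2.2 in the same form and state its margin.

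The cost is wording only; the evaluable 88 per group is unchanged. If the sponsor prefers a 95% interval, power at 88 should be restated as about 82%. If only non-inferiority is wanted, the equivalence wording must come out of the objective, Design, sample size and conclusion, and power at 88 should be restated with its alpha: 95% at one-sided 0.05 or 91% at one-sided 0.025. Whichever is chosen should be fixed before outcome data are examined.

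### Hypothesis 2.2 claims equivalent pain at 12 hours, but the plan states no margin, test or decision rule that could establish it

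*Combined protocol and SAP*

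**What the plan says.** Secondary Hypotheses, Hypothesis 2.2, predicts 12-hour VAS scores "at 12 hours after surgery that are equivalent compared to patients receiving TAP block with Bupivacaine only". Under Outcome Measure(s), the only primary outcome is "Pain score at 24 hours post-operative, using visual analogue scale (VAS), ranging from 1 to 10"; 12-hour pain is in the secondary list: "Pain scores at 12 hours, 48 hours, and 72 hours post-operatively".

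The Analytical Plan opens with: "Equivalency test with priori specified non-inferiority region will be used to assess primary outcome variables". Under Primary Hypothesis, the margin is introduced as "δ is non-inferiority margin, specified in advance based on clinical judgement" and set at 1.5. The two means it separates "are the population means for the outcome VAS measured at 24 hours after surgery". No margin is given for 12 hours.

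For other comparisons, the Analytical Plan names general or generalized linear regression for comparing outcomes between the arms. For univariate work on the primary and secondary outcomes, a t-test or "Wilcoxon two-sample test will be used for continuous variables". It adds: "Two-tailed p values will be calculated for all tests", with p < 0.05 as the threshold for significance.

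**The concern.** The hypothesis and the analysis ask different questions. An equivalence claim needs a margin and a rule that the data must satisfy. A difference test asks whether zero can be rejected, and failing to reject zero does not show that the true difference is small. A Wilcoxon p value says nothing about a margin on means.

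The only numerical threshold the plan supplies that could reach 12-hour pain is p < 0.05. Someone who has to report on Hypothesis 2.2 is then left with two poor options: take non-significance as support, or choose an equivalence method and margin after seeing the data. Under the first option, fewer or noisier 12-hour scores make equivalence easier to claim, which is the wrong direction. The plan expects 20% dropout and a per-protocol analysis, so some loss of 12-hour data is likely.

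**Working it through.** **Inputs.** From Sample Size: SD 3 per group, margin 1.5, true difference 0, alpha 0.05, power 90%, 88 per group, and 106 per group after allowing for 20% dropout. Losing 20% of 106 leaves 106 × 0.8 = 84.8, that is 84 or 85 per group. *Assumption:* the margin of 1.5 and SD of 3, which the plan gives for the 24-hour primary hypothesis, also apply at 12 hours. The documents give neither for 12 hours.

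**Step 1: reproduce the plan's own figure.** TOST at 5% per side with true difference 0, normal approximation:

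n = 2 × [SD × (z₀.₉₅ + z₀.₉₅) / margin]² = 2 × [3 × (1.645 + 1.645) / 1.5]² = 2 × 6.58² = 86.6, so 87.

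With the t distribution, the smallest n is 88, with power 0.903. This matches the plan. The alternatives do not: one-sided non-inferiority needs 69 (alpha 0.05) or 85 (alpha 0.025), and TOST at 2.5% per side needs 104 (normal approximation). The sample size therefore rests on a two-sided equivalence rule, equivalent to a 90% CI inside ±1.5.

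**Step 2: the two rules on the observed difference, 88 per group, SD 3.** Standard error = 3 × √(2/88) = 0.452.
- Non-significant in a two-sided t-test: |difference| < 1.974 × 0.452 = 0.893.
- Equivalent by TOST: |difference| < 1.5 − 1.654 × 0.452 = 0.752.

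Observed differences between 0.752 and 0.893 are non-significant but do not meet equivalence.

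**Step 3: chance of wrongly declaring equivalence at a true difference of 1.5.** For the non-significance reading this is F(t) − F(−t). Here F is the noncentral t distribution with 2n − 2 degrees of freedom and noncentrality 1.5 / (SD × √(2/n)), and t is the two-sided 5% critical value. With 88 per group the noncentrality is 1.5 / 0.452 = 3.32. The normal approximation gives Φ(1.96 − 3.32) = 8.7%; the exact value is 9.0%.

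| Analysed per group | SD | Non-significance reading | TOST |
|---|---|---|---|
| 106 | 3 | 4.8% | 5.0% |
| 88 | 3 | 9.0% | 5.0% |
| 85 | 3 | 10.0% | 5.0% |
| 84 | 3 | 10.4% | 5.0% |
| 70 | 3 | 16.4% | 5.0% |
| 60 | 3 | 22.5% | 5.0% |
| 88 | 4 | 30.4% | 5.0% |
| 88 | 2 | 0.1% | 5.0% |

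The rows for 70 and 60 are sensitivity cases. They need losses of 34% (1 − 70/106) and 43% (1 − 60/106), more than the plan's 20%. SDs of 2 and 4 are likewise assumptions, used to show the range.

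**Step 4: no true difference.** With 88 per group and SD 3, TOST claims equivalence in 90.3% of trials; the non-significance reading does so in 95%.

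**The case against.** The strongest reply is that the defect is silence. The plan nowhere says that a non-significant p value will count as equivalence. It assigns the equivalence test to the primary outcome without the word only, and Design calls the whole trial an equivalency trial. The t-test and Wilcoxon sentence follows one on identifying confounders and covers the primary outcome too, so it can be read as covariate screening. The regression sentence, which does address group comparison, would yield a mean difference that could be set against a margin.

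Much of this stands. A reader might infer that the plan reserves t-test and Wilcoxon for all non-primary outcomes, and that non-significance will be reported as equivalence. The text supports neither as a settled intention. But none of these readings supplies a 12-hour margin or an equivalence rule. Regression gives an estimate, and nothing states what the estimate must satisfy.

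A reader might also infer that a significant 12-hour difference would contradict equivalence. It need not. With SD 2 and 88 per group, observed differences from 0.595 to 1.001 are both significant and within ±1.5 by TOST. With a true difference of 0.5, about 33% of trials would show both. That is a real but small difference and not an error rate.

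Finally, the hypothesis is secondary, does not drive the sample size, and leaves the primary conclusion untouched. That limits the weight of the point but does not remove it.

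**Conclusion.** The point holds as a mismatch between hypothesis and analysis: Hypothesis 2.2 is a prespecified equivalence claim, and no analysis stated in the plan can establish it. This follows from the text and needs no numerical assumption.

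The size of the harm is conditional. It arises only if non-significance is taken as equivalence, and the figures borrow the 24-hour margin and SD. On that basis, false equivalence at the margin is roughly double the 5% that TOST allows, at the sample sizes the plan expects to analyse. There is no excess if all 106 per group contribute. It rises with more missing data or a larger SD and vanishes with an SD of 2. The plan should be changed; the matter is moderate and confined to a secondary hypothesis.

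**What to change.** State in the Analytical Plan that Hypothesis 2.2 is tested by a two-sided equivalence rule: estimate the 12-hour mean difference (from the linear model or t-based) and conclude equivalence only if its 90% CI lies wholly inside a prespecified 12-hour margin. The margin could be −1.5 to +1.5, if the investigators confirm that the 24-hour value applies at 12 hours.

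Write the rule out in full. A cross-reference to the primary hypotheses would not do, because H₀ and H₁ there are one-sided: they bound the difference from above only. Add that non-significant difference or Wilcoxon p values are not evidence for an equivalence claim. If equivalence at 12 hours is not really intended, rewording Hypothesis 2.2 as a difference hypothesis would also resolve the mismatch.

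The cost is a few sentences, with no new data and, under the assumed inputs, no more patients. The price is a somewhat harder claim: about 90% rather than 95% chance of success with 88 per group, SD 3 and no true difference.

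### Scheduled operation (sleeve or bypass) is neither a described stratification factor nor a prespecified covariate, so a modest and nearly free gain in precision is left to data-driven covariate screening

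*Combined protocol and SAP*

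**What the plan says.** The third inclusion criterion covers "Patients undergoing primary sleeve gastrectomy or roux-en-y gastric bypass". Subject Recruitment Methods adds that "Patients who are scheduled for sleeve gastrectomy or roux-en-y gastric bypass will be identified and recruited for the study", so the planned operation is known before allocation.

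Interventions and Interactions gives the allocation rule: schedules are produced in SAS "by using a masked block randomization procedure. Eligible patients will be randomized with a 1:1 ratio between the 2 groups", then managed and concealed through REDCap. No stratification factor or block size is mentioned.

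The Analytical Plan assigns the primary outcome to an equivalency test and names no covariate for it. It also allows general or generalized linear regression, univariate or multivariate, with confounders found by univariate analysis and both adjusted and unadjusted results reported. Operation type appears nowhere as a stratum, covariate or subgroup.

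The Sample Size section says "we assume standard deviation for each group is 3" and "the margin of equivalence is 1.5 on NRS", with a true difference of 0. It gives 88 per group for 90% power at alpha 0.05, raised to 106 for 20% dropout.

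**The concern.** The two operations are different procedures, and the type of operation could plausibly affect pain at 24 hours. A 1:1 block schedule balances the total number in each arm but not the number of sleeves and bypasses within each arm. If operation predicts pain, two things follow.

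- In any one trial, a chance difference in procedure mix moves an unadjusted arm difference.
- Between-operation variance stays in the error term of the equivalence test, although it could be removed.

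The plan's regression text does not settle this. Whether operation enters a model depends on a screening result seen after the data are in. If the adjusted and unadjusted analyses disagreed on equivalence, nothing says which one governs. At stake are a little precision and a clear primary analysis.

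**Working it through.** **Inputs from the documents.** SD 3 per group; margin 1.5; true difference 0; alpha 0.05; 88 per group before dropout and 106 after; 20% dropout; one centre; 1:1 allocation.

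**Assumptions, because the documents are silent.** The bypass share p is 30-50%. Operation shifts mean pain by d = 0.25 to 0.75 of the SD, that is 0.75 to 2.25 points. The SD of 3 is the total SD in the mixed population. Dropout is unrelated to operation.

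**1. The plan's own figure.** Two one-sided tests (TOST) at 0.05 each, t-based, with SE = 3 × √(2/88) = 0.452, give 90.3% power at 88 per group. The smallest n reaching 90% is 88, so the stated size reproduces with nothing done about operation.

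**2. Power at the number likely to be analysed.** 106 × 0.8 = 84.8, about 85 per arm. SE = 3 × √(2/85) = 0.460, and TOST power is 89.1%.

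**3. Chance imbalance in procedure mix.** The SD of the between-arm difference in bypass share is √(2p(1−p)/n). At n = 106:

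| p | SD | 95% range | Chance of a gap of 10 points or more |
|---|---|---|---|
| 0.3 | 6.3 points | ±12.3 points | 11% |
| 0.5 | 6.9 points | ±13.5 points | 15% |

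At 85 per arm the SD is 7.0 to 7.7 points and the chance of such a gap is 15-19%.

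**4. Effect of a 10-point gap on the arm difference.** Shift = 0.10 × operation effect. 0.10 × 0.75 = 0.075 and 0.10 × 2.25 = 0.225, so 0.08 to 0.23 points. That is 5% to 15% of the 1.5 margin and at most about half of the SE of 0.460.

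**5. Power with operation in the model.** Residual SD = 3 × √(1 − d²p(1−p)). At 85 per arm:

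| d | Residual SD (p = 0.3; 0.5) | Power (p = 0.3; 0.5) |
|---|---|---|
| none | 3 | 89.1% |
| 0.25 | 2.98; 2.98 | 89.5%; 89.6% |
| 0.50 | 2.92; 2.90 | 90.9%; 91.2% |
| 0.75 | 2.82; 2.78 | 93.0%; 93.7% |

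The gain runs from 89.5 − 89.1 = 0.4 to 93.7 − 89.1 = 4.6 percentage points.

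**6. Type I error without adjustment.** In 20,000 simulated trials (88 per arm, 50/50 mix, true difference at the 1.5 boundary), the unadjusted TOST declared equivalence in 5.1%, 5.1% and 5.2% of trials for operation effects of 0, 1 and 2 points. The simulation standard error is √(0.05 × 0.95/20,000) = 0.15 points, so the rate stays nominal.

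**The case against.** The strongest reply is that nothing is lost against the plan. Imbalance under concealed randomisation is random, and its contribution already sits in the standard error if the SD of 3 describes the mixed population. Steps 1 and 6 support this. The 89.1% starting figure comes from the dropout arithmetic and not from procedure mix. This part of the reply stands: the proper description is precision forgone, not power lost.

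The second reply is that the plan already permits adjustment. With 170 evaluable patients, screening at p < 0.05 would pick up operation with roughly 86-92% probability at d = 0.5 and over 99% at d = 0.75. It would often miss d = 0.25, where adjustment gains least. This stands in part. Screening would usually find a strong effect, but it remains data-driven and is not linked to the primary equivalency test.

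The third reply is that heterogeneity is already limited, since duodenal switch and concomitant hernia repair or cholecystectomy are excluded, and block technique and anaesthesia are standardised. That is true, but operation type remains a known procedural difference.

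A reader might infer more than the documents support:

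- **One unstratified list.** The text refers to schedules in the plural and is silent on strata. Silence supports only that stratification is not described.
- **Distorted opioid, nausea or length-of-stay comparisons.** No SD or operation effect is given for these outcomes, so no size can be stated.
- **Opposite arm differences in the two operations, hidden by pooling.** Nothing in the documents points to this, stratification would not remove it, and the trial is sized for the pooled comparison.

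**Conclusion.** The point holds as a minor matter of precision and prespecification. Operation is known before allocation, yet adjustment for it is neither guaranteed nor attached to the primary conclusion. The documents do not support reading this as bias, type I error inflation or a shortfall against the planned power, and no stated sample size changes.

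The benefit forgone is 0.4 to 4.6 percentage points of power on the primary outcome. Both ends rest on the assumed bypass share and operation effect, and the upper end needs a difference between operations of 2.25 points. If operation has little effect on pain, the gain is negligible. The case for acting is that the change costs almost nothing and fixes the primary model in advance.

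**What to change.** In the Analytical Plan, state that the 24-hour VAS difference and its equivalence interval come from a linear model with arm and scheduled operation as fixed terms, and that this model governs the primary conclusion. Include scheduled operation in the secondary outcome models too. For this factor, the prespecified term replaces univariate screening. Use the scheduled operation, because it is fixed before allocation. Label any results by operation as descriptive.

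If enrolment has not begun, also stratify the REDCap block schedule by scheduled operation, at 1:1 within each stratum. If it has begun, keep the existing schedule and adjust only. If the schedule is in fact already stratified, say so in the text.

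The cost is a sentence or two in the analysis plan and a minor amendment. Stratifying adds a second blocked schedule and one REDCap field, with the small downside of one incomplete block per stratum. No extra patients or visits are needed.
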